17 APPENDICES

Appendix A Guidance on contraceptive methods and collection of pregnancy information

Women Of Child Bearing Potential

A woman is considered of reproductive potential (WOCBP), ie, fertile, following menarche and until becoming postmenopausal unless permanently sterile. Permanent sterilization methods include hysterectomy, bilateral salpingectomy and bilateral oophorectomy.

Women of Child Bearing Potential must use one of the highly effective methods from the lists below:

Highly Effective Contraceptive Methods That Are User Dependent

Failure rate of <1% per year when used consistently and correctly^a

- Combined (estrogen- and progestogen-containing) hormonal contraception associated with inhibition of ovulation:
 - Oral,
 - Intravaginal,
 - Transdermal.
- Progestogen-only hormone contraception associated with inhibition of ovulation:
 - Oral,
 - Injectable.

Highly Effective Methods That Are User Independent

- Implantable progestogen-only hormone contraception associated with inhibition of ovulation.
- Intrauterine device (IUD).
- Intrauterine hormone-releasing system (IUS).

Sexual abstinence

Sexual abstinence is considered a highly effective method only if defined as refraining from heterosexual intercourse during the entire period of risk associated with the study drug. The reliability of sexual abstinence needs to be evaluated in relation to the duration of the study and the preferred and usual lifestyle of the subject.

NOTE:

- a. Typical use failure rates may differ from those when used consistently and correctly. Use should be consistent with local regulations regarding the use of contraceptive methods for subjects participating in clinical studies.

COLLECTION OF PREGNANCY INFORMATION

Female subjects who become pregnant

- The Investigator will collect pregnancy information on any female subject, who becomes pregnant while participating in this study.
- Information will be recorded on the appropriate form and submitted to the Sponsor within 24 hours of learning of a participant's pregnancy.
- Participant will be followed to determine the outcome of the pregnancy. The Investigator will collect follow-up information on participant and neonate, which will be forwarded to the Sponsor. Generally, follow-up will not be required for longer than 6 to 8 weeks beyond the estimated delivery date.
- Any termination of pregnancy will be reported, regardless of fetal status (presence or absence of anomalies) or indication for procedure.
- In this study pregnancy is considered to be an AESI and will be reported as such, any pregnancy complication or elective termination of a pregnancy will be reported as an AE or SAE.
- A spontaneous abortion is always considered to be an SAE and will be reported as such.
- Any SAE occurring as a result of a poststudy pregnancy which is considered reasonably related to the study treatment by the Investigator, will be reported to the Sponsor as described in [Section 10.4.1.3](#). While the Investigator is not obligated to actively seek this information in former study subjects, he or she may learn of an SAE through spontaneous reporting.

Male subjects with partners of reproductive potential who become pregnant

- The Investigator will attempt to collect pregnancy information on any female partner of a male study subject who becomes pregnant while participating in this study. This applies only to subjects who receive study treatment.
- After obtaining the necessary signed informed consent from the pregnant female partner directly, the Investigator will record pregnancy information on the appropriate form and submit it to the Sponsor within 24 hours of learning of the partner's pregnancy.
- Partner will also be followed to determine the outcome of the pregnancy. Information on the status of the mother and child will be forwarded to the Sponsor.
- Generally, follow-up will be no longer than 6 to 8 weeks following the estimated delivery date. Any termination of the pregnancy will be reported regardless of fetal status (presence or absence of anomalies) or indication for procedure.

Appendix B General guidance for the follow-up of laboratory abnormalities by sanofi

Immune thrombocytopenia

All patients will be monitored with monthly laboratory tests. The table below summarizes the minimum recommendations for ITP monitoring.

Summary of Minimum Recommendations for ITP Monitoring of All Patients

Test	Result	Action Items	Changes In Monitoring
Platelet Count	<LLN	Immediate repeat Hematology	If Repeat <LLN Weekly Hematology Until Stable*
	<100,000/ μL	Immediate repeat Hematology; Hematology Consult if confirmed	If Repeat <LLN Weekly Hematology Until Stable*
	<50,000/ μL	Immediate repeat Hematology; Emergency Hematology Consult if confirmed	If Repeat <LLN Weekly Hematology Until Stable*
Platelet Drop (but still within normal range)	100,000/ μL from prior	Investigator Notified	Investigator Discretion
	140,000/ μL from prior	Repeat Hematology	If Repeat < LLN Weekly Hematology Until Stable
ITP Signs or Symptoms	Any ITP Signs or Symptoms	Immediate site contact to determine further evaluation	As outlined above

*Weekly CBC Protocol: Weekly platelet counts for at least 8 weeks.

Return to Monthly when:

- Platelet counts × 8 are within the normal range (or)

- Platelet counts stabilize (8 consecutive readings $\geq 100,000/\mu\text{L}$ and average of last 4 counts \geq average of 4 prior counts)

After documenting stabilization, continue monthly monitoring as long as platelet counts remain $\geq 100,000/\mu\text{L}$; If a subsequent platelet count is confirmed to be $< 100,000$, the patient should resume weekly monitoring.

In addition to the above recommendations, the ongoing and long-term management of all patients with ITP will be subject to the clinical judgment of the treating hematologist.

Definition of ITP:For the purposes of this study, patients will be considered to have a diagnosis of ITP if they have all of the following:

- Normal Hgb.
- Normal WBC, though the differential will likely reflect lymphopenia as a result of the alemtuzumab treatment.
- No splenomegaly.
- No evidence of alternative nonautoimmune etiology of thrombocytopenia (eg, cytomegalovirus [CMV] infection).
- Normal peripheral smear except for a decrease in platelets without clumping.

AND either of the following:

- A confirmed platelet count equal to or above 50,000/ μ L but below 100,000/ μ L on at least 2 consecutive occasions over a period of at least 1 month, or,
- A confirmed platelet count below 50,000/ μ L without clumping documented on at least 2 consecutive occasions over any period of time.

It is recognized that confounding medical conditions may result in other abnormalities to the CBC, which can render diagnosis more difficult. **Nonetheless, any alemtuzumab-treated patient who meets the ITP criteria specified immediately above will receive no further alemtuzumab and will be immediately referred for hematologic consultation.**

If upon review of the peripheral smear platelet clumping is present indicative of pseudothrombocytopenia, the Hematology Panel should be repeated at a laboratory using an anticoagulant other than ethylenediamine tetraacetic acid (EDTA). In addition, examination of the peripheral smear should reveal a normal platelet estimate.

[figure not shown]
Anti-Glomerular Basement Membrane Disease

Alemtuzumab has also been associated with anti-GBM disease, which can cause a pulmonaryrenal syndrome known as Goodpasture’s disease. (Clatworthy, 2008, N Engl J Med; Coles, 2006, J Neurol) Anti-GBM disease is a rare autoimmune disorder in which circulating antibodies are directed against an antigen normally present in the basement membranes of renal glomeruli and pulmonary alveoli. The target antigen is the alpha-3 chain of type IV collagen. The resultant clinical syndrome encompasses a spectrum ranging from mild or no renal involvement to rapidly progressive glomerulonephritis. Patients may develop pulmonary hemorrhage. Signs and symptoms that commonly occur in patients with antiGBM disease include:

- Gross hematuria (red or tea colored urine).
- Hemoptysis.
- Edema (particularly lower extremity edema).
- Nonspecific symptoms can include malaise, fatigue, upper respiratory infection, rash.

[figure not shown]
In an effort to identify potential cases of antiGBM disease early, all patients will undergo monthly evaluation of serum creatinine levels alone or as part of a full chemistry panel and laboratory urinalysis (minimally including examination of protein and hemoglobin) with microscopy. Follow up of abnormal results will be guided by the algorithm below in 2 the figures below.

Monthly Urinalysis and Serum Creatinine

Abbreviations: SCr=Serum creatinine; GBM=glomerular basement membrane; UTI=urinary tract infection; WBC=white blood cells
*Morning urine preferred; false positive rate high during menses and one week after. If monthly urinalysis is positive for blood, SCr is normal, and the patient is menstruating, the urinalysis should be repeated one week following menses. If a patient has chronic microscopic hematuria or proteinuria that is being evaluated or already adequately evaluated, monthly surveillance should focus on changes in these levels and on SCr.

[figure not shown]
Follow-up of Abnormal Urine or Serum Creatinine Results

[figure not shown]

Abbreviations: SCr=serum creatinine

*Comparison is versus the lowest of pre-treatment values for that patient.

**While awaiting nephrology consult, consider repeating SCr in 2-3 days and refer emergently/consider hospitalization if SCr rising.

[figure not shown]
- In ANY CASE, FOLLOW** the instructions listed in the box below:
1. **INFORM** the Site Monitor who will forward the information to the Study Manager
 2. **INVESTIGATE** specifically for malaise with or without loss of consciousness, dizziness, and/or hypotension and/or episode of arrhythmia in the previous 72 hours; rule out muscular injury
 3. **PERFORM** the following tests:
 - LFTs: AST, ALT, alkaline phosphatase, total and conjugated bilirubin and prothrombin time / INR
 - CPK, serum creatinine, complete blood count
 - Anti-HAV IgM, anti-HBc IgM (HBV-DNA if clinically indicated), anti-HCV and HCV RNA, anti-CMV IgM and anti-HEV IgM antibodies
 - Depending on the clinical context, check for recent infection with EBV, herpes viruses, and toxoplasma
 - Hepatobiliary ultrasonography (or other imaging investigations if needed)
 4. **CONSIDER** Auto-antibodies: antinuclear, anti-DNA, anti-smooth muscle, anti-LKM
 5. **CONSIDER** consulting with hepatologist
 6. **CONSIDER** patient hospitalisation if INR>2 (or PT<50%) and/or central nervous system disturbances suggesting hepatic encephalopathy
 7. **MONITOR LFTs after discontinuation of IMP:**
 - As closely as possible (or every 48 hours) until stabilization, then every 2 weeks until return to normal/baseline or clinical resolution.
 8. **FREEZE** serum sample (5ml x 2)
 9. **In case of SUSPICION of GILBERT Syndrome**, a DNA diagnostic test should be done

*If unable to retest in 72 hours, use original lab results to decide on further reporting/monitoring/discontinuation.

Note:

[figure not shown]
- “Baseline” refers to ALT sampled at baseline visit; or if baseline value unavailable, to the latest ALT sampled before the baseline visit. The algorithm does not apply to the instances of increase in ALT during screening.
- See [Section 10.4](#) for guidance on safety reporting.
- Normalization is defined as ≤ ULN or baseline value, if baseline value is >ULN.

ACUTE RENAL FAILURE

Acute renal failure is to be recorded as an AE only if at least 1 of the criteria listed in the general guidelines for reporting AEs in [Section 10.4.5](#) is met.

SUSPICION OF RHABDOMYOLYSIS

Suspicion of rhabdomyolysis is to be recorded as an AE only if at least 1 of the criteria in the general guidelines for reporting AEs in [Section 10.4.5](#) is met.

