- E 27. Active infection, eg, deep-tissue infection, that the Investigator considers sufficiently serious to preclude study participation.
- E 28. In the Investigator's opinion, patient is at high risk for infection (eg, indwelling catheter, dysphagia with aspiration, decubitus ulcer, history of prior aspiration pneumonia or recurrent urinary tract infection).
- E 29. Infection with hepatitis B, C viruses (positive serology, but not due to hepatitis immunization).
- E 30. History of tuberculosis (TB)/latent TB (unless it is documented by a specialist that the patient has been adequately treated and can now start treatment with a biologic agent).
- E 31. Testing will be conducted for human papillomavirus (HPV) infection as and when recommended by local public health authorities. If the testing is positive, the patient may be eligible after the condition has resolved as per the Investigator opinion (eg, follow-up HPV test is negative or cervical abnormality has been effectively treated).
- E 32. Any other illness or infection (latent or active) that, in the Investigator's opinion, could be exacerbated by study medication.

Laboratory Parameters

- E 33. Confirmed platelet count <LLN of the evaluating laboratory at Screening or documented at <100 000/ μ L within the past year on a sample without platelet clumping.
- E 34. CD4+, CD8+, or CD19+ (ie, absolute CD3+CD4+, CD3+CD8+, or CD19+/ mm^3) count <LLN at Screening; if abnormal cell count(s) return to within normal limits, eligibility may be reassessed.
- E 35. Absolute neutrophil count <LLN at Screening; if abnormal cell count returns to within normal limits, eligibility may be reassessed.

Note: If the treating physician suspects out-of-range cell count results are based upon issues of sample transportation or environmental conditions, the treating physician may request a repeat sample to be evaluated locally to confirm the patient is not excluded from the trial. If out-of-range cell counts are not confirmed through evaluations performed locally, the treating physician should

document (in source data and in a CRF comment) that the central laboratory results are considered falsely exclusive, and proceed to enroll the patient.

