10.1.10 Visit 16/M12 (second course of alemtuzumab)

Visit 16 (M12) can occur within -7 days or +30 days of the scheduled visit.

The following assessments should be done as listed in the study flow chart:

- Physical examination and vital signs.
- Perform Tanner staging.
- Blood and urine samples collection for clinical laboratory assessments including pregnancy test (for females of childbearing potential), thyroid function test, urinalysis and for ADA.
- Blood samples collection for lymphocyte phenotyping.
- Blood samples collection for PK and immune markers (optional).
- Assess and confirm eligibility for alemtuzumab administration.
- Alemtuzumab will be administered as daily IV infusion on 3 consecutive days in a supervised medical setting. Calculation of the dose used will be based on patient weight. Observation for infusion reactions is recommended during and for at least 2 hours (based on local requirements) after alemtuzumab infusion.
- The Investigator or designee will contact the IVRS to obtain a treatment kit number.
- On days of Alemtuzumab infusion, and 1 hour prior to the infusion, H1 antagonist IV should be administered immediately followed by 30mg/kg or 1000mg IV methylprednisolone (whichever is lower). H2 antagonist medications and NSAID/antipyretic should be administered on the 3 consecutive days of alemtuzumab

administration as needed. Study patients should also receive antiviral prophylaxis for herpetic viral infection beginning on Day 1 and continuing for a minimum of 1 month. If diphenhydramine IV is not available, an equivalent H1 antagonist can be used at an equivalent dosing, via IV route. If no H1 antagonist is available in IV formulation, an oral formulation of an equivalent compound can be used at an equivalent dosing, 2 hours prior to infusion.

- Vital signs during infusion days will be monitored.
- AE/SAE will be monitored (if any).
- Concomitant medication will be checked and reported (if any).

The following infusion management procedures must be utilized for each infusion and each treatment course:

- Pre-infusion :

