10.3.3 List of criteria for permanent treatment discontinuation

The patients may withdraw from treatment with the IMP if they decide to do so, at any time and irrespective of the reason, or this may be the Investigator's decision. All efforts should be made to document the reason(s) for treatment discontinuation and this should be documented in the e-CRF in the EOTP Visit.

Patients must discontinue the IMP for the following reasons:

- Pregnancy or intention for pregnancy.
- At patient/parents request (ie, withdrawal of the consent for treatment).
- If, in the Investigator's opinion, continuation with the administration of the IMP would be detrimental to the patient's well-being.
- Intercurrent condition that requires discontinuation of the IMP (eg, laboratory abnormalities, please refer to decision tree in [Appendix B](#)).
- Life threatening events (such as such as myocardial ischemia, pulmonary alveolar hemorrhage, HLH,...)
- At the specific request of the Sponsor.

Any abnormal laboratory value will be immediately repeated for confirmation (within 24 hours if possible), before making a decision of permanent discontinuation of the IMP for the concerned patient.

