10.4.1.3 Adverse event of special interest

Any AESI will be reported to the Sponsor in the same timeframe as SAEs, ie, within 24 hours, as detailed in [Section 10.4.4](#).

An AESI is an AE (serious or nonserious) of scientific and medical concern specific to the Sponsor's product or program, for which ongoing monitoring and immediate notification by the Investigator to the Sponsor is required. Such events may require further investigation in order to characterize and understand them. Adverse events of special interest may be added, modified or removed during a study by protocol amendment.

The following AE will be considered as an AESI:

- Hypersensitivity or anaphylaxis.
- Pregnancy occurring in a female patient entered in the clinical trial. It will be qualified as an SAE only if it fulfills one of the seriousness criteria (see [Section 10.4.1.2](#)). Follow-up of the pregnancy in a female participant is mandatory until the outcome has been determined.
- Symptomatic overdose (serious or nonserious) with IMP/non-investigational medicinal product (NIMP).
 - An overdose (accidental or intentional) with the IMP is an event suspected by the Investigator or a nurse and defined as an increase of at least 30% of the dose to be administered in the specified duration or if the dose is administered in less than half the recommended duration of administration,
 - An overdose with the NIMP is an event suspected by the Investigator or spontaneously notified by the patient (not based on systematic pills count) and defined as at least twice the intended dose within the intended therapeutic interval, adjusted according to the tested drug,
 - Of note, asymptomatic overdose has to be reported as a standard AE.
- Increase in ALT (see the "Increase in ALT" flow diagram in [Appendix B](#) of the protocol).
- Other product specific AESI(s):
 - Autoimmune mediated conditions including but not limited to autoimmune encephalitis, cytopenias, ITP, autoimmune hepatitis, nephropathies including anti-glomerular basement membrane (GBM) disease, thyroid disorders and acquired Hemophilia A (see [Appendix B](#))
 - Temporally associated* pulmonary alveolar hemorrhage
 - Temporally associated* myocardial ischemia, myocardial infarction
 - Temporally associated* stroke
 - Temporally associated* cervicocephalic arterial dissection
(* Temporally associated: 1 to 3 days after the last infusion)
 - HLH,
 - Progressive multifocal leukoencephalopathy (PML)
 - Pneumonitis,

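### The ITP definition that bars further alemtuzumab uses two non-overlapping platelet bands, so some series that stay below 100,000/µL but cross 50,000/µL can meet neither limb.

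*Protocol*

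**What the plan says.** Appendix B (Immune thrombocytopenia, definition of ITP) sets common conditions on haemoglobin, white cells, spleen, alternative causes and smear. It then requires either of two platelet limbs:

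- **Limb 1:** a confirmed count at or above 50,000/µL and below 100,000/µL, "on at least 2 consecutive occasions over a period of at least 1 month".
- **Limb 2:** a confirmed count below 50,000/µL, "without clumping documented on at least 2 consecutive occasions over any period of time".

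The consequence is mandatory: "any alemtuzumab-treated patient who meets the ITP criteria specified immediately above will receive no further alemtuzumab".

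The monitoring table in the same appendix requires a repeat test after a low count. For a count below 50,000/µL the action is "Immediate repeat Hematology; Emergency Hematology Consult if confirmed". A repeat below the lower limit of normal starts weekly counts for at least 8 weeks. The text does not say whether the immediate repeat is an occasion in its own right or only confirms one.

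**The concern.** A stopping rule for low platelets should be monotonic: lowering a count should never take a patient out of it. This rule is not. A count below 50,000/µL does not qualify for limb 1, so it interrupts a limb 1 run, yet a single such occasion does not meet limb 2. A child whose counts stay below 100,000/µL for two months, dipping now and then below 50,000/µL, can meet neither limb. A child with higher, steadier counts meets limb 1 and is stopped.

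Section 4 reports serious ITP in about 1% of patients treated in the MS trials and a fatal index case. At stake are the automatic bar on further dosing and whether the child is classified as having study-defined ITP.

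**Working it through.** The plan gives no figure to reproduce. The check is an exact enumeration of the rule, with no distributional assumption.

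**Inputs (Appendix B).** Band limits 50,000 and 100,000/µL; two consecutive occasions for either limb; at least 1 month for limb 1 and any interval for limb 2; weekly counts for at least 8 weeks. I take nine weekly visits (days 0 to 56), all counts below 100,000/µL, the common conditions met, and at least one count on each side of 50,000/µL. Write L for below 50,000 and M for 50,000 to under 100,000. One month is 28 days, or 30 to 31 days as the alternative.

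**Reading A: the repeat only confirms, so each visit is one occasion.**
- Mixed patterns: 2^9 − 2 = 510.
- Limb 2 fails if no two L are adjacent. Limb 1 fails if no run of M is long enough. Five weekly counts span 28 days, so runs must be at most 4. At 30 to 31 days six counts are needed (35 days), so runs may be up to 5.
- Patterns meeting neither limb: **66 of 510** at 28 days, **77 of 510** at 30 to 31 days.

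**Reading B: the repeat is its own occasion, taken one day later.**
- Each visit is M-M, L-M (the low count rebounds) or L-L. Patterns, excluding all M-M and all L-L: 3^9 − 2 = 19,681.
- Any L-L visit meets limb 2 at once, so an escaping pattern contains only M-M and L-M visits.
- At 28 days, at most 4 M-M visits may precede the first L-M, and at most 3 may follow each L-M. Let f(n) be the number of ways to fill n visits starting with an L-M. Then f(n) = f(n−1) + f(n−2) + f(n−3) + f(n−4) with f(0) = 1, giving f(5) to f(9) = 15, 29, 56, 108, 208. The total is 208 + 108 + 56 + 29 + 15 = **416 of 19,681**.
- At 31 days the limits become 5 and 4, and the recursion has five terms. f(4) to f(9) = 8, 16, 31, 61, 120, 236, with total 236 + 120 + 61 + 31 + 16 + 8 = **472 of 19,681**.

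**Reading C: as B, and an unconfirmed low reading is ignored.** An L-L visit meets limb 2. Otherwise every low reading drops out and the M run is unbroken for 8 weeks, meeting limb 1. Escapes: **0**.

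**Explicit weekly series over 8 weeks (thousand/µL).**

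| Series | Reading A | Reading B |
|---|---|---|
| 80 throughout | limb 1 met | limb 1 met |
| 80-80-80-48 repeated | neither | limb 2 if the 48 repeats below 50; neither if it rebounds to 55 |
| 48-60 repeated | neither | limb 2 if a 48 repeats below 50; neither if each rebounds to between 50 and 100 |

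**After removing the 50,000 floor from limb 1.** Every series above lies wholly below 100,000/µL and spans at least a month, so limb 1 is met. Escapes: **0** under A, B and C.

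**The case against.** The strongest reply is that the gap depends on how the text is read. Both limbs speak of a confirmed count, the table above them says that confirmation is by immediate repeat, and limb 2 accepts any interval. On that view a 48 repeated at 46 meets limb 2 at once, and a 48 repeated at 55 is not a confirmed low count and should not break a limb 1 run. That is Reading C, where nothing escapes. It is a reasonable reading, but the protocol does not choose it, and a mandatory stop should not rest on an unstated convention across about 50 planned sites.

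The second reply is that other protections exist, and most of this stands:

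- Courses are planned only at Months 0 and 12 (section 8.1), so the bar acts in practice on the Month 12 course.
- Section 10.3.3 requires stopping for an "Intercurrent condition that requires discontinuation of the IMP (eg, laboratory abnormalities" or similar), and also where the investigator judges continuation detrimental.
- A confirmed count below 100,000/µL brings a haematology consult, and below 50,000/µL an emergency one.
- Section 10.1.10 has the site "Assess and confirm eligibility for alemtuzumab administration" before the second course. If section 7.2 is applied there, E 33 covers counts below 100,000/µL "within the past year on a sample without platelet clumping", with no 50,000 floor. The protocol does not expressly say that E 33 is re-applied at Month 12. Section 10.3.1 re-applies the selection criteria only after a temporary discontinuation.
- Reporting is not lost: section 10.4.1.3 lists "Autoimmune mediated conditions including but not limited to autoimmune encephalitis, cytopenias, ITP" among the events of special interest.
- Section 10.4.6 refers to a thrombocytopenia flow chart, which may be among the figures not reproduced in the available text and may contain a further stopping rule.

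These points limit the consequence. None of them, as far as the available text shows, restores the automatic bar or the ITP classification for a series that falls between the limbs. Finally, the pattern counts weight all sequences equally and say nothing about frequency; that is correct, and they are not offered as frequencies.

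**Conclusion.** The concern holds. Read literally, the two limbs leave a gap, and a lower count can remove a patient from a mandatory stopping rule. The gap is narrow: most crossing series still meet a limb. With nine weekly counts the escapes are 66 to 77 of 510 patterns under Reading A, 416 to 472 of 19,681 under Reading B (all with every low count rebounding on repeat), and none under Reading C. The protocol gives no basis for a frequency in children. The result assumes that the common ITP conditions are met and that no flow chart among the missing figures overrides the text. The change is worth making because it corrects a safety rule at little cost, not because the safeguards as a whole fail.

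**What to change.** In Appendix B, delete the 50,000/µL lower bound from limb 1, so that any confirmed count below 100,000/µL qualifies, and keep its persistence requirement. Leave limb 2 unchanged; it still gives the faster route for very low counts. Stating whether the immediate repeat counts as an occasion would also help sites apply the rule consistently, although the gap closes without it.

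This is a one-line edit at the next amendment and needs no new tests. The downside is that slightly more patients may be classified as ITP and stopped. That is consistent with a rule that already stops a child steady at 80,000/µL.
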